8.1 Evaluation/definition of Primary Outcome

See section 6 “reliability of data” for the calculation of survival time for the primary objective.

8.2 Statistical Methods Used for Analysis of Primary Outcome

In the first instance, the primary outcome will be analysed to achieve the primary objectives assuming there is no interaction between treatments.

Kaplan-Meier curves will be produced and logrank analysis will be used to compare the time to primary outcome between those receiving aspirin and those not and also between those receiving low PPI and high dose PPI. A significance level of $p=0.05$ will be used. An accelerated failure time (AFT)

AspECT

A phase III randomised study of Aspirin and Esomeprazole chemoprevention in Barrett's metaplasia

Funded by CR-UK, MRC, UHL and NCI

ISRCTN No.85156844

model will be constructed for each co-primary to adjust the treatment comparisons for age, length of Barrett's metaplasia and presence of intestinal metaplasia (as used in the minimisation procedure). To increase precision, the alternative co-primary will be added into the model. An AFT model was chosen so that the estimates of the effect are in terms of a time ratio (ratio of expected survival times in the aspirin/no aspirin comparison or low PPI/high PPI comparison).

The logrank results will be presented in a table

	total	Number of events	Logrank and p value
Aspirin Aspirin No aspirin			
PPI Low PPI High PPI			

The time ratios will be presented with 95% confidence intervals and will form the definitive analysis for the primary aim.

If proportional hazards assumptions are valid, a Cox regression model with just aspirin treatment and then another with just PPI treatment will be presented. A Cox model for each coprimary considering the effect of treatment whilst adjusting for age, length of Barrett's Metaplasia and presence of intestinal metaplasia will be also be presented. To increase precision, the alternative co-primary will be added into the model. These models will give hazard ratios with associated 95% confidence intervals. These are provided for comparison with other research.

All centres will be analysed together. It is expected that either STATA, SAS, SPLUS or other similar statistical software will be used for the analysis.

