### 13.3 Randomisation – Stratification and Standardisation

Randomisation was by minimization with a random element. The variables were:

Length of Barrett's – tongue, <2cm, ≥2cm and ≤3cm, >3cm and ≤8cm, >8cm

Age - 18-49, 50-59, 60-69, ≥70

Intestinal metaplasia – yes, no

These may be risk factors for the development of dysplasia and adenocarcinoma. Through using minimization with the same variables, women and men are randomised separately, as are those only taking part in the PPI randomisation.

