2.6 Randomisation

Randomisation is by minimisation using age split into four groups and length of Barrett's metaplasia split into three groups. There is a random component, with the patient having an 80% chance of being assigned the treatment that reduces the imbalance.

Age

- 40-49
- 50-59
- 60-69

AspECT

A phase III randomised study of Aspirin and Esomeprazole chemoprevention in Barrett's metaplasia

Funded by CR-UK, MRC, UHL and NCI

ISRCTN No.85156844

70-75

Length of Barrett's metaplasia

≤3cm

>3 and ≤8cm

>8cm

Initially the trial accrued only males. From Sept 2005, there are separate minimisation routines running for males and females.

**** Change in 2007

Limit on age to be removed and Barrett's from 1cm to be included***

Then

Age

18-49

50-59

60-69

≥70

Length of Barrett's metaplasia

<2cm

≥2cm and ≤3cm

>3 and ≤8cm

>8cm

2.6.1 *** Change 25th Feb 2008 ***

IM to be added as stratification factor

Tongue of Barretts to be added as a level in length

Individuals participating only in the PPI randomisation are randomised in a separate routine (same stratification)

Gender already separate routine

Then

Age

18-49

50-59

60-69

≥70

Length of Barrett's metaplasia

Tongue of Barretts

<2cm

≥2cm and ≤3cm

AspECT

A phase III randomised study of Aspirin and Esomeprazole chemoprevention in Barrett's metaplasia

Funded by CR-UK, MRC, UHL and NCI

ISRCTN No.85156844

>3 and ≤8cm
>8cm
IM
Yes
No

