8.6 Sensitivity analysis

As specified in section 7 using PP sample and variables as randomised.

A Kaplan-Meier plot will be drawn with a line for each of the four treatment groups to look for a visual sign of interaction between the treatments. An interaction term will also be added to AFT and COX models containing both of the treatment main effect to test for significance (although this will have low power). If statistically significant interaction is found, the results will also be presented for aspirin within each PPI treatment group and for PPI within each aspirin group.

The estimate of the treatment effect in AFT and Cox models will be adjusted for presence of helicobacter.

AFT and Cox models will be adjusted for gender as well as the minimisation variables.

AFT and Cox models will be adjusted for NSAID and for Cox Inhibitor use. Use will be defined as more than 1 month continuously and as more than 6 months continuously.

AFT and Cox models with stratifying variables will be redone using actual Barrett's length at baseline.

The primary analysis will be repeated using all oesophageal cancers instead of just adenocarcinoma of the oesophagus.

The primary analysis will be repeated censoring follow-up when patients start taking NSAID.

The primary analysis for PPI will be repeated censoring patients when they start taking another medicine for Barrett's (data in EOT form reasons for withdrawal 'other' and in Follow Up form in 'treatments for Barrett's other than esomeprazole').

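### Sex and PPI-only entry were separate randomisation streams, but the definitive model and logrank test leave both out; including them is a small, free improvement

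*SAP*

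**What the plan says.** **Randomisation.** SAP 2.6 records that the trial first accrued only men and then: "From Sept 2005, there are separate minimisation routines running for males and females". Protocol 13.3 lists three minimisation variables (Barrett's length, age, intestinal metaplasia) and adds that "women and men are randomised separately, as are those only taking part in the PPI randomisation". SAP 2.6.1, dated 25 February 2008, adds intestinal metaplasia as a factor and also describes the PPI-only routine.

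**Primary analysis.** In SAP 8.2, "logrank analysis will be used to compare the time to primary outcome between those receiving aspirin and those not", and likewise for low against high dose PPI; no strata are given. The AFT "model will be constructed for each co-primary to adjust the treatment comparisons for age, length of Barrett's metaplasia and presence of intestinal metaplasia", and the reason for that list is in the words "presence of intestinal metaplasia (as used in the minimisation procedure". The other randomised treatment is added for precision. The SAP then fixes the status of this model: "The time ratios will be presented with 95% confidence intervals and will form the definitive analysis for the primary aim". The adjusted Cox model has the same covariates. Protocol 14 gives the same three adjustment variables.

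**Where sex does appear.** SAP 8.6: "AFT and Cox models will be adjusted for gender as well as the minimisation variables". SAP 8.5 repeats the analysis in each sex. SAP section 9 fits AFT and Cox models for gender as a prognostic factor, then refits them with treatment included.

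**PPI-only patients.** SAP section 7 includes them in the PPI comparison and excludes them from the aspirin comparison. No model in SAP 8.2 or 8.6 has a term for them.

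**The concern.** The usual principle is that the main analysis reflects the way patients were randomised. Separate routines force treatment balance within each stream. If the streams differ in risk and the analysis ignores them, the stated standard error is, in theory, slightly too large and the test slightly conservative.

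Three features of the plan make the omission look unintended:

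- Intestinal metaplasia became a minimisation factor only on 25 February 2008, a year before recruitment ended on 25 February 2009 (SAP 2.3), yet it is in the model. Sex had been separated since September 2005 and is not.
- The documents regard sex as relevant to risk. Protocol 1.5 gives a 3 to 1 male excess for oesophageal adenocarcinoma, and Protocol 13.2 counts being female among the reasons for a lower assumed conversion rate.
- SAP 8.2 already adds the other treatment to gain precision. Sex would serve the same purpose.

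PPI-only patients may also differ in risk. They include people on aspirin for previous heart disease or stroke (Protocol 8.2) and people with a contraindication to aspirin (SAP 2.4).

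What is at stake is which of several planned models has authority. If models with and without sex fell on opposite sides of 0.05, the plan would rely on the one that ignores a randomisation stratum. Secondary endpoints that reuse the primary method (SAP section 9) inherit the choice.

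**Working it through.** **1. The plan's own figure.** SAP 2.5.3 states 196 events and 2224 patients for a hazard ratio of 1.5, 80% power and two-sided 5%, with (1.960 + 0.842)² = 7.849.

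- Schoenfeld: 4 × 7.849 / (ln 1.5)² = 191 events.
- Freedman: 7.849 × [(1 + 1/1.5)/(1 − 1/1.5)]² = 7.849 × 25 = 196.2, or 197 rounded up.
- Power with 196 events: Φ(½ × √196 × ln 1.5 − 1.960) = Φ(0.878) = 81.0%.
- Patients: control rate 1% a year, 3 years' accrual, 10 further years, and 10% loss treated as exponential over 13 years. Event probabilities are 0.1038 (control) and 0.0705 (treated), mean 0.0871. 196/0.0871 is about 2250, within 3% of 2224.

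The stated figures reproduce. The formula has no covariate term, so adding sex does not change them.

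**2. Simulation of the omission.**

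Inputs from the documents: 2012 men and 501 women (Protocol 2), average control rate 1% a year, treatment hazard ratio 1/1.5.

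Assumptions: male:female hazard ratio for the composite of 1 to 3; 1:1 allocation within sex; Weibull AFT (the SAP names no distribution); censoring at 8 to 10 years; 10% lost uniformly over 10 years; all 2513 patients in one comparison. Age, length, intestinal metaplasia and PPI-only entry were not simulated.

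There were 2000 runs per setting for power and 4000 under the null. Shorter follow-up than the plan's 10 further years gives about 182 events, so power is near 76%.

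| Male:female HR | AFT power, without / with sex | Time ratio, without / with | Logrank power, unstratified / stratified |
|---|---|---|---|
| 1 | 75.80 / 75.75% | 1.496 / 1.496 | 76.55 / 76.65% |
| 1.5 | 76.15 / 76.25% | 1.505 / 1.506 | 76.85 / 76.90% |
| 2 | 76.00 / 76.25% | 1.503 / 1.504 | 76.65 / 76.70% |
| 3 | 75.05 / 75.40% | 1.502 / 1.503 | 76.00 / 76.35% |

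The largest gain is 0.35 points. The time ratio moves by at most 0.001. The hazard ratio from the same Weibull fit also moves by at most 0.001 (0.6671 to 0.6661 at a sex ratio of 3).

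Type I error for the AFT model, without / with sex, is 4.9/4.9, 4.8/4.8, 4.5/4.6 and 4.7/4.8%. For the logrank test it lies between 4.8 and 5.2% in both forms. The Monte Carlo standard error is about 1 point for each power figure and 0.35 points for each type I error. Paired differences are more precise, because both analyses use the same simulated trials.

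**3. Hand check at a sex ratio of 3.** Few patients have an event, so sex can explain little of the outcome variance.

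- Overall event proportion: 181/2513 = 0.0720. Proportion of women: 501/2513 = 0.199.
- Taking the hazard ratio as approximately the risk ratio: women 0.0720/(0.199 + 3 × 0.801) = 0.0277; men 0.0831.
- Share of variance between the sexes: 0.199 × 0.801 × (0.0831 − 0.0277)² / (0.0720 × 0.9280) = 0.0073.
- Z increases by a factor of 1/√(1 − 0.0073) = 1.0037. At 76.0% power the mean Z is about 2.67, and the gain is about 0.3 points, in line with the table.

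**4. A different scenario.** With a composite rate of 1.16 + 0.85 = 2.01% a year (Protocol 13.2), an assumed 8 years of follow-up and an assumed treatment hazard ratio of 0.75, 4000 simulated trials per setting give these mean |Z| values, unstratified and sex-stratified: 2.613 and 2.619 (sex ratio 1.5), 2.615 and 2.627 (2), 2.571 and 2.593 (3). That is 0.2%, 0.5% and 0.9% more. Power goes from 74.1 to 74.1%, 74.4 to 74.8% and 73.5 to 73.9%.

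**The case against.** The strongest defence has four parts.

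- **The SAP is consistent.** A reader might infer that 8.2 claims to adjust for every randomisation factor and fails to. The text does not support that. The three variables it names are exactly those that Protocol 13.3 lists as minimisation variables; sex was a separate routine using those same variables, and 8.6 names gender apart from them. The logrank test makes no claim to adjust. This part stands in full: what remains is an omitted stratum, not a misstatement.
- **A sex-adjusted result will be reported anyway**, through 8.6, 8.5 and section 9. This also stands. The open matter is only which of two nearly identical estimates is called definitive.
- **Sex may be weakly prognostic here.** The 3 to 1 ratio is for adenocarcinoma, while mortality makes up 1.16 of the 2.01% a year, about 58%. Protocol 13.2 gives its reduced conversion rate to a mixed group, of whom women are only part, and says that differing rates are unpublished. This stands, and it is why the sex ratio is treated as an assumption.
- **Adding sex alone would not follow the randomisation**, because PPI-only patients also had their own routine. This is right, and it widens the remedy rather than removing the point.

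**Conclusion.** The point holds as a minor specification gap. The definitive AFT model, the supporting Cox model and the logrank test omit sex, and in the PPI comparison also PPI-only entry, although patients were randomised separately by both.

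For sex, the cost of the omission is about 0 to 0.4 points of power and at most 0.001 in the time ratio, with AFT type I error at or slightly below 5%. These figures rest on an assumed composite sex hazard ratio of 1 to 3, a Weibull model and no other covariates. For PPI-only entry no size can be given, because the documents state neither the number of such patients nor their event rate.

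Two stronger inferences should be resisted. A reader might expect the time ratio to be materially pulled towards no effect; the simulation shows no shift that matters. A reader might also expect a larger gain for adenocarcinoma because its sex ratio is larger; that was not calculated, and the hand check shows that the gain also depends on how common the event is. No sex ratio is given for high grade dysplasia or mortality.

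The case for change is that the main analysis would follow the randomisation at no data cost, not that the result would be expected to differ.

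**What to change.** In SAP 8.2, and in Protocol 14 if it is amended:

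1. Add sex to the definitive AFT model and the adjusted Cox model for both co-primaries, and to the section 9 secondary models that reuse the primary method.
2. Add an indicator for PPI-only randomisation to the PPI models. Coding aspirin allocation there as aspirin, no aspirin, or not randomised to aspirin achieves this, and also settles how these patients enter the aspirin term.
3. Stratify the logrank test by sex for the aspirin comparison, and by sex and PPI-only entry for the PPI comparison.
4. In SAP 8.6, replace the gender-adjusted run with the model that omits these terms, as the sensitivity analysis.

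The cost is a few lines of text. SAP 6.6 expects gender for all patients from randomisation, the randomisation stream should be in the randomisation records, and the gender-adjusted model is already planned. The change should be made before treatment comparisons are seen; if later, it should be reported as a deviation, as the SAP introduction requires.

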#### *Exploratory sample size statement October 2008*

Due to protocol amendments and an expected restriction on the number of patients to be recruited, an exploratory sample size is presented at the request of the Funders. Since the trial recruited until the end of February 2009 in the UK rather than to the number calculated in the original sample size, this calculation should be considered as a guide to the power and treatment effect size the trial should achieve.

This exploratory sample size is calculated as per the original sample size, but with

- Annual rate of conversion of 1% (allowing for the composite primary endpoint of all-cause mortality and conversion to adenocarcinoma and conversion to high grade dysplasia.)

*Justification:* Using the National Statistics figures for 2005 based on the age and gender structure of the first 2046 patients recruited to AspECT gives a mortality rate in a year of 1.16%.

Using the UK Barrett's conversion rate to adenocarcinoma of at least 0.98% per year without treatment for 60% of the sample and 40% with a lower conversion rate of 0.66% (due to being female, have tongues of Barrett's metaplasia or only 1cm of Barrett's, or being <45 years old). Differing rates are not published for these patients so a rate of two thirds the UK conversion rate has been used) i.e. 0.85% conversion rate without treatment over the whole sample.

No good estimates of rates for conversion to high grade dysplasia for the UK could be found.

In this population, it is unlikely that the event rate for the composite primary endpoint in the control arm will be less than 1%.

- Hazard ratio as in colorectal cancer
- No adjustment for compliance
- the follow-up increased to 10 years (subject to available funding)

Apart from limited recruitment and checking the event rate using the age/sex structure, no information or estimates from the current trial are used.

A total of 2224 patients (approximately 556 in each intervention group) will allow us to detect a difference in conversion rates of 0.34% per year between low dose and high dose PPI and aspirin or no aspirin. This sample size was calculated using ARTMENU in STATA release 10.0 based on the following:

- Patients will be recruited over 3 years and followed up for a further 10 years (subject to available funding)
- Exponential time to conversion with a constant event rate of at least 1% per year without treatment

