## 14 STATISTICAL ANALYSIS PLAN

All analyses will be on an intention-to-treat basis. This means that patients will be analysed as they are randomised irrespective of the treatment actually received. The intention-to-treat population will include all patients who have given their informed consent and for whom there is confirmation of successful allocation of a randomisation number. All participants who receive one dose of IMP will be evaluable for the safety analysis.

It is therefore important that every effort is made to encourage patients, including those patients who do not receive/complete their allocated treatment, to attend for follow-up clinic visits and complete the questionnaires to avoid bias in the analysis of the results.

Analyses will be carried out at the 5% level of significance. The main analysis will be a comparison of A+B v C+D (aspirin v no aspirin) and A+C v B+D (high v low dose PPI) assuming no treatment interaction. Logrank analysis will be used to compare the time from randomisation to primary outcome (high grade dysplasia, adenocarcinoma of the oesophagus or death from all causes) for the different treatment comparisons. An Accelerated Failure Time (AFT) model will be constructed to adjust the treatment comparisons for length of Barrett's metaplasia, age and occurrence of intestinal metaplasia (as used in the minimisation procedure). This will be repeated with Cox regression model for comparison with other research. Interim analyses of the primary aim were planned at 2 and 4 years after the end of recruitment.

A number of patients will be randomised to the PPI comparison only; hence they will only be included in the analysis of the effect of high vs low dose PPI.

Sensitivity analysis will use the per protocol sample and the possibility of interaction between the two treatments will be investigated.

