2.5.3 Exploratory sample size statement October 2008

Due to protocol amendments and an expected restriction on the number of patients to be recruited, an exploratory sample size is presented at the request of the Funders. Since the trial will recruit until end Dec 2008 in the UK and possibly until the end of June in Canada rather than to the number calculated in the original sample size, this calculation should be considered as a guide to the power and treatment effect size the trial should achieve.

This exploratory sample size is calculated as per the original sample size, but with

- Annual rate of conversion of 1% (allowing for the composite primary endpoint of all cause mortality and conversion to adenocarcinoma and conversion to high grade dysplasia.)

Justification: Using the National Statistics figures for 2005 based on the age and gender structure of the first 2046 patients recruited to AspECT gives a mortality rate in a year of 1.16%.

Using the UK Barrett's conversion rate to adenocarcinoma of at least 0.98% per year without treatment for 60% of the sample and 40% with a lower conversion rate of 0.66% (due to being

AspECT

A phase III randomised study of Aspirin and Esomeprazole chemoprevention in Barrett's metaplasia

Funded by CR-UK, MRC, UHL and NCI

ISRCTN No.85156844

female, have tongues of Barrett's metaplasia or only 1cm of Barrett's, or being <45 years old. Differing rates are not published for these patients so a rate of two thirds the UK conversion rate has been used) ie 0.85% conversion rate without treatment over the whole sample.

No good estimates of rates for conversion to high grade dysplasia for the UK could be found.

In this population, it is unlikely that the event rate for the composite primary endpoint in the control arm will be less than 1%.

- HR as in colorectal cancer
- No adjustment for compliance
- the follow-up increased to 10 years

Apart from limited recruitment and checking the event rate using the age/sex structure, no information or estimates from the current trial are used.

A total of 2224 patients (196 events) (approximately 556 in each intervention group) will allow us to detect a difference in conversion rates of 0.34% per year between low dose and high dose PPI and aspirin or no aspirin. This sample size was calculated using ARTMENU in STATA release 10.0 based on the following:

- Patients will be recruited over 3 years and followed up for a further 10 years

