- Exponential time to conversion with a constant event rate of at least 1% per year without treatment
- Conversion hazard ratio (drug response) of control to treatment is 1.5 (1 year conversion rate 1% no or standard treatment vs 0.66% in the treated patients)
- Power = 80% (2-sided test at 5% level of significance)
- No interaction between the effects of aspirin and PPI interventions
- A 10% loss to follow-up from Office of National Statistics flagging

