6.2 Baseline Comparability of Randomised Groups

A table of baseline data for all patients, each of the four intervention groups and the groups for the main comparisons will be given. This will include

Variable at baseline	Low PPI no aspirin	Low PPI and aspirin	High PPI no aspirin	High PPI and aspirin	TOTAL
Length of Barrett's metaplasia at rand (strata for minimisation and median(range), cm)					
Age (strata for minimisation, median(range), years)					
Gender Male Female					
Intestinal metaplasia Yes No					
Retrospective patient Yes No					
Duration of Barrett's pre randomisation Median (range), years					
Alcohol use None some					

AspECT

A phase III randomised study of Aspirin and Esomeprazole chemoprevention in Barrett's metaplasia

Funded by CR-UK, MRC, UHL and NCI

ISRCTN No.85156844

Variable at baseline	Low PPI no aspirin	Low PPI and aspirin	High PPI no aspirin	High PPI and aspirin	TOTAL
(For some group, median(iq range),units per week)					
Smoker No never Ex Yes current					
Myocardial Infarction Yes No					
Angina Yes No					
Coronary Intervention Yes No					
Stenosis Yes No					
Cardiac catheterisation Yes No					
Cerebrovascular Yes No					
TIA Yes No					
Peripheral Vascular Disease Yes No					
Diabetes Yes No					

AspECT

A phase III randomised study of Aspirin and Esomeprazole chemoprevention in Barrett's metaplasia

Funded by CR-UK, MRC, UHL and NCI

ISRCTN No.85156844

Variable at baseline	Low PPI no aspirin	Low PPI and aspirin	High PPI no aspirin	High PPI and aspirin	TOTAL
Hypertension Yes No					
Hyperlipidaemia Yes No					

This table will be repeated with columns of no aspirin, aspirin, low PPI and high PPI. Those taking part in the PPI only randomisation will not appear in the no aspirin/aspirin columns since they did not take part in the aspirin randomisation.

Numbers (with percentages) for binary and categorical variables and means (and standard deviations), or medians (with range) for continuous variables will be presented. There will be no tests of statistical significance nor confidence intervals for differences between randomised groups on any baseline variable.

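### SAP 8.2 most naturally enters age in the definitive AFT model as the four minimisation bands; stating continuous age would recover a little precision without dropping any patient

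*SAP*

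**What the plan says.** SAP 8.2 names the adjusted AFT time ratio, with its 95% confidence interval, as the definitive result for each co-primary comparison. The covariates are age, length of Barrett's metaplasia and "presence of intestinal metaplasia (as used in the minimisation procedure"), plus the other randomised treatment, added for precision. Protocol 14 has the same adjustment, "occurrence of intestinal metaplasia (as used in the minimisation procedure"), and says the model is repeated as a Cox regression.

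SAP 2.6 and Protocol 13.3 show that the minimisation used age in four bands, finally 18-49, 50-59, 60-69, and 70 and over. SAP 8.2 does not state outright how age is coded, and no planned analysis names continuous age.

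Exact age is held. The baseline table in SAP 6.2 has a row for "Age (strata for minimisation, median(range), years"), and Appendix 2 lists age from the randomisation form among the primary-aim variables. SAP 6.6 says the minimisation factors will be known for every patient.

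On the endpoint, Protocol 13.2 says the age and sex structure of the first 2046 patients "gives a mortality rate in a year of 1.16" per cent. It puts conversion to adenocarcinoma at 0.85% a year and has no estimate for high grade dysplasia.

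Smoking, cardiac and vascular history and diabetes are in the SAP 6.2 table. Smoking, diabetes and patient cardiac history are also predictors in the secondary cardiac and cancer models of SAP 9. None enters the primary models of 8.2 or the sensitivity models of 8.6.

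**The concern.** Death rises steeply with age, and bands treat everyone inside them as equal. With the log-hazard slopes of 0.07, 0.09 and 0.11 per year assumed below, patients aged 60 and 69 share a band, yet their death hazards differ by exp(9 × 0.07) = 1.9, exp(9 × 0.09) = 2.2 or exp(9 × 0.11) = 2.7 times. The oldest band has no upper limit.

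Since death is the largest quantified component, variation that could be explained is left unexplained in the definitive estimate. The form of age is also left to a parenthesis, and SAP 2.6 shows that the outer bands changed during recruitment (40-49 to 18-49; 70-75 to 70 and over). At stake are a slightly wider confidence interval and an avoidable coding choice in the definitive model.

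**Working it through.** **1. Share of death.** 0.6 × 0.98 + 0.4 × 0.66 = 0.852% a year for adenocarcinoma. 1.16 / (1.16 + 0.85) = 58% of the quantified rate.

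**2. The plan's own figure.** Inputs from SAP 2.5.3: "Power = 80% (2-sided test at 5% level of significance"); "Conversion hazard ratio (drug response) of control to treatment is 1.5"; "Exponential time to conversion with a constant event rate of at least 1% per year without treatment"; "Patients will be recruited over 3 years and followed up for a further 10 years"; 10% loss; 196 events in 2224 patients.
- Freedman: (1.96 + 0.8416)² × ((1.5 + 1)/(1.5 − 1))² = 7.849 × 25 = 196.2, so 197 rounded up, against 196 stated.
- Schoenfeld: 4 × 7.849 / (ln 1.5)² = 191.
- Patients: uniform accrual and exponential loss of 10% over 13 years give a mean event probability of 0.0871 to 0.0875. Then 196 events need 2239 to 2250 patients, against 2224. The design is reproduced.

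**3. Simulated gain.** Weibull AFT fitted by maximum likelihood, 2500 trials per scenario, N = 2224, accrual, follow-up and loss as above, hazard ratio 1/1.5. Control rates were 1% (the plan's) and 2.01% (1.16 + 0.85).

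Assumptions not in the documents:
- age mean 59, SD 11;
- smoking 18%, cardiac history 12%, diabetes 8%;
- weak/mid/strong effects on death: log-hazard per year of age 0.07/0.09/0.11; hazard ratios 1.4/1.8/2.5 for smoking and for cardiac history, and 1.4/1.6/2.0 for diabetes;
- a weaker age effect on conversion;
- the Weibull form, since the SAP names no distribution.

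Information gain = (mean Z of new model / mean Z of banded model)² − 1, from unrounded values. Power = Φ(mean Z − 1.96). Fuller means continuous age plus the three factors.

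| Rate, scenario | Events | Z banded | Z continuous age | Z fuller | Gain, age | Gain, fuller | Power banded / age / fuller |
|---|---|---|---|---|---|---|---|
| 1%, weak | 190 | 2.689 | 2.692 | 2.697 | 0.3% | 0.6% | 0.767 / 0.768 / 0.769 |
| 1%, mid | 187 | 2.634 | 2.648 | 2.657 | 1.1% | 1.8% | 0.750 / 0.754 / 0.757 |
| 1%, strong | 182 | 2.571 | 2.598 | 2.625 | 2.1% | 4.2% | 0.730 / 0.738 / 0.747 |
| 2.01%, weak | 359 | 3.681 | 3.698 | 3.705 | 0.9% | 1.3% | 0.957 / 0.959 / 0.959 |
| 2.01%, mid | 349 | 3.590 | 3.619 | 3.647 | 1.6% | 3.2% | 0.948 / 0.951 / 0.954 |
| 2.01%, strong | 333 | 3.457 | 3.506 | 3.557 | 2.9% | 5.9% | 0.933 / 0.939 / 0.945 |

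- The fuller model narrows the confidence interval by 0.2 to 1.8% and adds 0.2 to 1.7 power points. Raw rejection shares, which are noisier, rose by 0.1 to 2.5 points.
- For scale, banded adjustment already gains 2.8 to 11% over no adjustment.
- Two further simulation sets, with hazard ratios and event numbers that are not the plan's, gave 0.9 to 3.7% (Cox, hazard ratio 1/1.3, 400 to 425 events) and 0.3 to 2.6% (Weibull AFT, hazard ratio 1/1.4, N = 2513) for continuous age alone. The Cox set gave 1 to 7.5% for a fuller model that also included hypertension.

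**4. Missing covariates.** Fuller model, complete cases only, mid scenario:

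| Rate | Banded, all patients | 0% missing | 2% | 5% | 10% |
|---|---|---|---|---|---|
| 1% | 0.747 | 0.753 | 0.745 | 0.729 | 0.706 |
| 2.01% | 0.947 | 0.953 | 0.950 | 0.943 | 0.930 |

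The power gain is gone at 2% missing in the first row and by 5% in the second. In the second Weibull set (500 trials per scenario, 5 to 10% missing), a missing category kept a gain of 0.5 to 6.1% in all 12 runs; complete-case analysis gave −10.0% to +1.2%.

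**5. Bias towards no effect.** In the runs of step 3 the mean log time ratio differed between banded and fuller models by at most 0.004 (0.403 against 0.407), about 1%. In a separate AFT check with a true value of 0.262, banded against full was 0.264 against 0.268 (mid) and 0.254 against 0.262 (strong), or 1 to 3%.

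**The case against.** Adjusting for the factors used at randomisation is coherent, pre-specified and consistent with the protocol. The parenthesis may say which variables enter rather than how they are coded, and in SAP 8.2 it is attached to the AFT sentence but not to the Cox one. The trial is open-label and the primary aim was analysed at two interims, so late additions to the definitive model could look chosen from the data. Most of this stands as a reason for restraint. It argues for stating the form of age and for keeping undocumented covariates out of the definitive model. It does not argue for bands over exact age.

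Four stronger readings are tempting, and the documents do not support them:
- **All the unused covariates are free precision.** SAP 6.6 promises completeness only for the minimisation factors, SAP 8.4 expects no imputation, and the Document History records shortened forms on which previous aspirin use was no longer collected. Missingness for smoking, cardiac history and diabetes is not given.
- **Both co-primary tests lose power.** In SAP 8.2 the 5% level is attached to the logrank comparison, which is unadjusted and unaffected.
- **The time ratio is materially diluted.** Attenuation from omitted covariates is chiefly a hazard-ratio problem; step 5 shows 1 to 3% at most for the AFT.
- **The predictors of death are used only descriptively.** SAP 9 uses several of them in its secondary logistic models.

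**Conclusion.** The point holds as a small, cheap improvement. On the natural reading, the definitive model uses banded age when exact age is available for everyone. Continuous age alone is worth about 0.3 to 4% effective information: 0.3 to 2.9% at hazard ratio 1.5, with 3.7% the highest value in any set. On 2513 patients, 0.3 to 2.9% equals about 8 to 73 patients (0.003 × 2513; 0.029 × 2513). With the three further factors the total is about 0.6 to 6%, and power rises by at most about 2 points. No sample size or design decision changes.

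The direction was the same in every simulation. The size rests on the assumed age spread, hazard slopes, prevalences and Weibull form. The aspirin comparison excludes the PPI-only patients, so its absolute power is lower, but its relative gain should be similar.

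**What to change.** - **SAP 8.2:** state that age at randomisation enters the AFT and Cox models as a continuous term (linear plus quadratic, or a spline with its knots named), fixed before the final analysis. Keep the banded model as a sensitivity analysis. The cost is one sentence and one or a few parameters; no patient is dropped, and randomisation and data collection are unaffected.
- **SAP 8.6:** add one adjusted AFT and Cox model with smoking status, any cardiac or vascular history, and diabetes, using a missing category so that every randomised patient stays in. Report how many values are missing. The cost is a few parameters and a missing-data rule, and this part should not be described as free.
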